5.4.3 Confirmation and Date of Recurrence

The first date when recurrence was observed is taken into account regardless of the method of assessment. Therefore recurrence will be declared for any lesion when:

- If recurrence is unequivocal (eg, multiple new measurable lesions, symptomatic or requires initiation of subsequent treatment prior to confirmation) confirmation with histology/cytology should be attempted, but not required.
- If recurrence is equivocal, lymph node only, solitary lesion, or in the urothelial tract, confirmation with histology/cytology must be attempted. Confirmation of a defined lesion on cystoscopy requires transurethral biopsy and, if necessary, retrograde study and biopsy. If risk of biopsy is too high or biopsy not feasible, either a follow-up CT or MRI scan showing progressive disease or PET/CT demonstrating unequivocal FDG uptake must confirm recurrence. Follow-up (confirmatory) scan should occur 4-12 weeks after the initial scan. The date of initial scan showing recurrence will count as recurrence.
- Any pathological evidence of malignancy denotes recurrence (eg, if scans never attempted). Positive urine cytology (eg, positive Urovision or similar urine assay) alone does not constitute the basis for recurrence of disease. Tumor markers or auto-antibodies alone cannot be used to document recurrence.
- If both pathology and imagining were done and recurrence/malignancy confirmed, the date of recurrence is the date to which ever examination came first.
- When biopsies are performed for the purpose of documenting urothelial cancer recurrence, the pathology reports are to be submitted to corelab for a collect and hold. This includes biopsies performed during cystoscopy.

5.6.1 Tumor Tissue Specimens

Pre-treatment tumor tissue specimens in the form of a paraffin embedded block or a minimum of 10 unstained slides will be submitted for central PD-L1 IHC assessment prior to randomization. These biopsy samples should be from the most recently resected site of disease. PD-L1 stained tissue sections will be assessed by a pathologist and membranous PD-L1 expression scored in tumor and immune cells if a minimum of a hundred (100) evaluable tumor cells are present. Subjects with tumor samples containing less than a hundred tumors cells per tissue section will not be randomized, but subjects with positive, negative or indeterminate (membrane staining is obscured by high cytoplasmic staining or melanin content) PD-L1 expression will be stratified based on their expression. PD-L1 expression level or indeterminate status (as assessed by central lab) will be logged into IVRS by the central laboratory prior to randomization. Allow approximately 10 business days from the date of shipping for tissue to be received and processed. Allow for this time in planning for randomization. If PD-L1 expression results have not been logged into IVRS by the central laboratory, randomization will not be allowable through IVRS.

In addition, this pre-treatment tumor sample may be used to assess other putative predictive biomarkers of nivolumab efficacy and/or to better characterize the tumor-immune microenvironment within the resected tissue. Various molecular markers with potential predictive value for the treatment of urothelial cancer with nivolumab and other immunotherapies are currently under investigation and may be assessed in this study. These tumor tissue biomarkers include, but are not limited to PD-L1, PD-L2, TILs or subpopulations of TILs and a Th1 immune mRNA expression signature. In addition, other methods of measuring tumor PD-L1 expression may also be assessed. These pre-treatment tumor samples may also be used to further characterize the tumor-immune microenvironment through assessment of markers that may be associated with the efficacy of nivolumab, including but not limited to other T cell checkpoint receptors and ligands (eg, Lag-3, Tim-3) intratumoral immune cell subsets, including macrophages, natural killer (NK) cells and B cells.

Tumor tissue samples may also be collected upon recurrence. This sample may be used for the assessment of markers implicated in resistance to immunotherapeutic agents, including but not limited to other T cell checkpoint receptors and ligands (eg, Lag-3, Tim-3) and intratumoral immune cell subsets, including but not limited to, T regulatory cells and myeloid derived suppressor cells. These samples may also be used to investigate the effect of nivolumab on the expression of potentially relevant predictive and/or prognostic urothelial cancer biomarkers. Both the pre-treatment tumor sample and the sample collected upon recurrence may be retrospectively profiled for gene expression/mutation status, as well as for the expression of other immune or urothelial cancer related genes, RNAs, miRNA and proteins, or for the presence of immune cell populations using a variety of methodologies inclusive of, but not limited to IHC, qRT-PCR, genetic mutation detection and fluorescent in-situ hybridization (FISH).

[REDACTED]

6 ADVERSE EVENTS

An *Adverse Event (AE)* is defined as any new untoward medical occurrence or worsening of a preexisting medical condition in a clinical investigation subject administered study drug and that does not necessarily have a causal relationship with this treatment. An AE can therefore be any unfavorable and unintended sign (such as an abnormal laboratory finding), symptom, or disease temporally associated with the use of study drug, whether or not considered related to the study drug.

The causal relationship to study drug is determined by a physician and should be used to assess all adverse events (AE). The causal relationship can be one of the following:

Related: There is a reasonable causal relationship between study drug administration and the AE.

Not related: There is not a reasonable causal relationship between study drug administration and the AE.

The term "reasonable causal relationship" means there is evidence to suggest a causal relationship.

Adverse events can be spontaneously reported or elicited during open-ended questioning, examination, or evaluation of a subject. (In order to prevent reporting bias, subjects should not be questioned regarding the specific occurrence of one or more AEs.)

6.1 Serious Adverse Events

A *Serious Adverse Event (SAE)* is any untoward medical occurrence that at any dose:

- results in death
- is life-threatening (defined as an event in which the subject was at risk of death at the time of the event; it does not refer to an event which hypothetically might have caused death if it were more severe)

- requires inpatient hospitalization or causes prolongation of existing hospitalization (see **NOTE** below)
- results in persistent or significant disability/incapacity
- is a congenital anomaly/birth defect
- is an important medical event (defined as a medical event(s) that may not be immediately life-threatening or result in death or hospitalization but, based upon appropriate medical and scientific judgment, may jeopardize the subject or may require intervention [eg, medical, surgical] to prevent one of the other serious outcomes listed in the definition above.) Examples of such events include, but are not limited to, intensive treatment in an emergency room or at home for allergic bronchospasm; blood dyscrasias or convulsions that do not result in hospitalization.) Potential drug induced liver injury (DILI) is also considered an important medical event. (See [Section 6.6](#) for the definition of potential DILI.)

Suspected transmission of an infectious agent (eg, pathogenic or nonpathogenic) via the study drug is an SAE.

Although pregnancy, overdose, cancer, and potential drug induced liver injury (DILI) are not always serious by regulatory definition, these events must be handled as SAEs. (See [Section 6.1.1](#) for reporting pregnancies).

Any component of a study endpoint that is considered related to study therapy (eg, death is an endpoint, if death occurred due to anaphylaxis, anaphylaxis must be reported) should be reported as SAE (see [Section 6.1.1](#) for reporting details).

NOTE:

The following hospitalizations are not considered SAEs in BMS clinical studies:

- a visit to the emergency room or other hospital department < 24 hours, that does not result in admission (unless considered an important medical or life-threatening event)
- elective surgery, planned prior to signing consent
- admissions as per protocol for a planned medical/surgical procedure
- routine health assessment requiring admission for baseline/trending of health status (eg, routine colonoscopy)
- medical/surgical admission other than to remedy ill health and planned prior to entry into the study. Appropriate documentation is required in these cases
- admission encountered for another life circumstance that carries no bearing on health status and requires no medical/surgical intervention (eg, lack of housing, economic inadequacy, caregiver respite, family circumstances, administrative reason).
- Admission for administration of anticancer therapy in the absence of any other SAEs (applies to oncology protocols)

6.1.1 Serious Adverse Event Collection and Reporting

Sections 5.6.1 and 5.6.2 in the Investigator Brochure (IB) represent the Reference Safety Information to determine expectedness of serious adverse events for expedited reporting. Following the subject's written consent to participate in the study, all SAEs, whether related or not related to study drug, must be collected, including those thought to be associated with protocol-specified procedures. All SAEs must be collected that occur during the screening period and within 100 days of discontinuation of dosing.

Following the subject's written consent to participate in the study, all SAEs, whether related or not related to study drug, must be collected, including those thought to be associated with protocol-specified procedures. All SAEs must be collected that occur during the screening period and within 100 days of discontinuation of dosing. Subjects who are randomized and never treated with study drug, must have SAEs collected for 30 days from the date of randomization. If applicable, SAEs must be collected that relate to any later protocol-specified procedure (eg, a follow-up skin biopsy).

The investigator should report any SAE that occurs after these time periods and that is believed to be related to study drug or protocol-specified procedure.

An SAE report should be completed for any event where doubt exists regarding its seriousness.

If the investigator believes that an SAE is not related to study drug, but is potentially related to the conditions of the study (such as withdrawal of previous therapy or a complication of a study procedure), the relationship should be specified in the narrative section of the SAE Report Form.

SAEs, whether related or not related to study drug, and pregnancies must be reported to BMS (or designee) within 24 hours of becoming aware of the event. SAEs must be recorded on the SAE Report Form; pregnancies on a Pregnancy Surveillance Form (electronic or paper forms). The preferred method for SAE data reporting collection is through the eCRF. The paper SAE/pregnancy surveillance forms are only intended as a back-up option when the eCRF system is not functioning. In this case, the paper forms are to be transmitted via email or confirmed facsimile (fax) transmission to:

SAE Email Address: Refer to Contact Information list.

SAE Facsimile Number: Refer to Contact Information list.

For studies capturing SAEs through electronic data capture (EDC), electronic submission is the required method for reporting. The paper forms should be used and submitted immediately, only in the event the electronic system is unavailable for transmission. When paper forms are used, the original paper forms are to remain on site.

SAE Telephone Contact (required for SAE and pregnancy reporting): Refer to Contact Information list.

If only limited information is initially available, follow-up reports are required. (Note: Follow-up SAE reports should include the same investigator term(s) initially reported.)

If an ongoing SAE changes in its intensity or relationship to study drug or if new information becomes available, a follow-up SAE report should be sent within 24 hours to the BMS (or designee) using the same procedure used for transmitting the initial SAE report.

All SAEs should be followed to resolution or stabilization.

6.2 Nonserious Adverse Events

A *nonserious adverse event* is an AE not classified as serious.

6.2.1 Nonserious Adverse Event Collection and Reporting

The collection of nonserious AE information should begin at initiation of study drug. Nonserious AE information should also be collected from the start of a placebo lead-in period or other observational period intended to establish a baseline status for the subjects.

Nonserious AEs should be followed to resolution or stabilization, or reported as SAEs if they become serious (see [Section 6.1.1](#)). Follow-up is also required for nonserious AEs that cause interruption or discontinuation of study drug and for those present at the end of study treatment as appropriate. All identified nonserious AEs must be recorded and described on the nonserious AE page of the CRF (paper or electronic).

All nonserious adverse events (not only those deemed to be treatment-related) should be collected continuously during the treatment period and for a minimum of 100 days following the last dose of study treatment.

Every adverse event must be assessed by the investigator with regard to whether it is considered immune-mediated. For events which are potentially immune-mediated, additional information will be collected on the participant's case report form.

Completion of supplemental CRFs may be requested for AEs and/or laboratory abnormalities that are reported/identified during the course of the study.

6.2.2 Adverse Events of Interest

Definition of immune-mediated adverse events (IMAEs)

Immune-mediated AEs are specific events (that include pneumonitis, diarrhea/colitis, hepatitis, nephritis/renal dysfunction, rash, and endocrine (adrenal insufficiency, hypothyroidism/thyroiditis, hyperthyroidism, diabetes mellitus, and hypophysitis) for which subjects received immunosuppressive medication for treatment of the event, with the exception of endocrine events (hypothyroidism/thyroiditis, hyperthyroidism, hypophysitis, diabetes mellitus, adrenal insufficiency), which are included regardless of treatment since these events are often managed without immunosuppression.

Immune-mediated adverse events are AEs consistent with an immune-mediated mechanism or immune-mediated component for which non-inflammatory etiologies (eg, infection or tumor progression) have been ruled out. IMAEs can include events with an alternate etiology which were exacerbated by the induction of autoimmunity. Information supporting the assessment will be collected on the participant's case report form. IMAEs include events, regardless of causality,

occurring within 100 days of the last dose. IMAEs are limited to subjects who received immunosuppressive medication for treatment of the event, with the exception of endocrine events (hypothyroidism/thyroiditis, hyperthyroidism, hypophysitis, diabetes mellitus, adrenal insufficiency), which are included regardless of treatment since these events are often managed without immunosuppression.

Table 6.2.2-1 below provides a summary of the IMAEs category and their respective PTs.

Table 6.2.2-1: Preferred Terms Included in Analysis of IMAEs to Support Warnings and Precautions

IMAE Category	PTs included under IMAE Category
Pneumonitis	Pneumonitis, Interstitial lung disease
Diarrhea/Colitis	Diarrhea, Colitis, Enterocolitis
Hepatitis	Hepatotoxicity, Hepatitis, Hepatitis acute, Autoimmune hepatitis, AST increased, ALT increased, Bilirubin increased, ALP increased
Adrenal insufficiency	Adrenal insufficiency
Hypothyroidism/Thyroiditis	Hypothyroidism, Thyroiditis Thyroiditis acute (collapsed with thyroiditis for frequency), Autoimmune thyroiditis (collapsed with thyroiditis for frequency)
Hyperthyroidism	Hyperthyroidism
Hypophysitis	Hypophysitis
Diabetes mellitus	Diabetes mellitus, Diabetic ketoacidosis
Nephritis and renal dysfunction	Nephritis, Nephritis allergic, Tubulointerstitial nephritis, Acute renal failure, Renal failure, Increased creatinine
Rash	Rash, Rash maculopapular

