## 6 STUDY PERIODS, TREATMENT REGIMENS AND POPULATIONS FOR ANALYSES

### 6.1 Study Periods

- Baseline period:
  - Baseline evaluations or events will be defined as evaluations or events that occur before the date and time of the first dose of study treatment. Evaluations (laboratory tests and vital signs) on the same date and time of the first dose of study treatment will be considered as baseline evaluations. Adverse Events (AEs) on the same date and time of the first dose of study treatment will not be considered as pre-treatment events.
  - In cases where the time (onset time of event or evaluation time and dosing time) is missing or not collected, the following definitions will apply:
    - ◆ Pre-treatment AEs will be defined as AEs with an onset date prior to but not including the day of the first dose of study treatment;
    - ◆ Baseline evaluations (laboratory tests and vital signs) will be defined as evaluations with a date on or prior to the day of first dose of study treatment.
  - If there are multiple valid assessments on or prior to the first dose of study treatment:
    - [REDACTED]
    - [REDACTED]
    - ◆ For PD-L1, among the biopsy samples records taken prior to or on first dose date (and time if collected), identify first those with quantifiable test result. If there are no records with quantifiable test result, then select those with indeterminant result (“INDETERMINATE”). If there are no records with indeterminant test result, then select those with unavailable result (“NOT EVALUABLE”). If there are no records with unavailable test result, then select those with not reported or not available result (all other records). The latest record will be used as the baseline in the analyses. If there is more than one record for the latest date, then choose the one with the greatest specimen ID.
    - [REDACTED]

- Post baseline period:
  - On-treatment AEs will be defined as AEs with an onset date and time on or after the date and time of the first dose of study treatment (or with an onset date on or after the day of first dose of study treatment if time is not collected or is missing). For subjects who are off study treatment, AEs will be included if event occurred within a safety window of 30 days (or 100 days depending on the analysis) after the last dose of study treatment. No “subtracting rule” will be applied when an AE occurs both pre-treatment and post-treatment with the same preferred term and grade.

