## 6.3 Populations for Analyses

- Enrolled subjects: All subjects who signed the informed consent form and obtained a subject number.
- Randomized subjects: All subjects who were randomized through the IRT.
- Randomized subjects with PD-L1 expression  $\geq 1\%$ : All subjects who were randomized through the IRT with baseline PD-L1 expression  $\geq 1\%$  as stratification factor (source IVRS).
- Treated subjects: All randomized subjects who received at least one dose of any study treatment (nivolumab or placebo).
- Treated subjects with PD-L1 expression  $\geq 1\%$ : All randomized subjects with baseline PD-L1 expression  $\geq 1\%$  as stratification factor (source IVRS) who received at least one dose of any study treatment (nivolumab or placebo).

█ [REDACTED]

█ [REDACTED]

Adverse events leading to dose reduction are AEs with action taken regarding study drug(s) = “Dose was reduced”.

Adverse events will be coded using the Medical Dictionary for Regulatory Activities (MedDRA), and the most recent version of the dictionary at the time of the database lock will be used. Adverse events results will be graded for severity using NCI Common Terminology Criteria for Adverse Events (CTCAE) and the most recent version of the criteria at the time of the database lock will be used.

In the AE summary tables, unless otherwise specified, subjects will be counted only once at the Preferred Term (PT), only once at the System Organ Class (SOC), and only once at subject level for the counting of total number of subjects with an AE. The AE tables will be sorted by the SOCs and then PTs. SOC will be ordered by descending frequency overall and then alphabetically. PTs will be ordered within SOC by descending frequency overall and then alphabetically. The sorting will be done based on the ‘Any Grade’ column of the experimental arm when arms are presented side-by-side.

Unless otherwise specified, the AE summary tables will be restricted to on-treatment events regardless of the causality.

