### **7.4.3.2 Subsequent Cancer Therapy**

The following summary table will be provided overall and by treatment group as randomized in all randomized subjects as well as all randomized subjects with PD-L1 expression  $\geq 1\%$ :

- Number and percentage of subjects receiving subsequent cancer therapies including the following categories:
  - Number and percentage of subjects receiving subsequent systemic therapy, overall, by type of therapy and by drug name:
    - ◆ Number and percentage of subjects receiving subsequent immunotherapy (anti-PD1 agents, anti-PD-L1 agents, anti-CTLA-4 agents and others), overall and by drug name
    - ◆ Number and percentage of subjects receiving subsequent BCG or other intravesical chemotherapy (approved and investigational), overall and by drug name
    - ◆ Number and percentage of subjects receiving subsequent other agents (approved and investigational), overall and by drug name
  - Number and percentage of subjects receiving subsequent surgery for treatment of tumors, overall, by type of surgery
  - Number and percentage of subjects receiving subsequent radiotherapy for treatment of tumors
  - Number and percentage of subjects receiving any combination of the above

A by-subject listing of subsequent cancer therapy will also be produced.

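### The protocol's immune-mediated AE definition and the visible SAP rules have no cut at subsequent checkpoint-inhibitor therapy; a supplementary truncated table would settle the attribution cheaply

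*Protocol*

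**What the plan says.** Protocol 6.2.2 sets three conditions for an IMAE besides the list of terms.

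- **Cause:** "IMAEs include events, regardless of causality". The causes to be excluded are non-inflammatory ones: the events are those "for which non-inflammatory etiologies (eg, infection or tumor progression) have been ruled out".
- **Time and treatment:** "occurring within 100 days of the last dose. IMAEs are limited to subjects who received immunosuppressive medication for treatment of the event".
- **Exception:** endocrine events count even without immunosuppressive treatment.

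The visible SAP rules are built the same way. For subjects off treatment, SAP 6.1 includes events "within a safety window of 30 days (or 100 days depending on the analysis) after the last dose of study treatment". The adverse-event text that follows SAP 6.3 says that, unless otherwise specified, "the AE summary tables will be restricted to on-treatment events regardless of the causality". The person-time formula there runs to 30 or 100 days after last dose and does not end at a new therapy.

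Two other parts of the plan bear on this. Protocol 3.5 makes recurrence a reason to stop study drug, so the post-dose window opens when next-line therapy becomes likely. SAP 7.4.3.2 plans to tabulate "Number and percentage of subjects receiving subsequent immunotherapy (anti-PD1 agents, anti-PD-L1 agents, anti-CTLA-4 agents and others"), so such therapy is expected and recorded.

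**The concern.** Immune toxicity from a second checkpoint inhibitor passes every condition in 6.2.2. It has an immune mechanism, no non-inflammatory cause explains it, it is treated with immunosuppressants (or is endocrine and needs no treatment), and it can fall within 100 days of the last study dose. Nothing in the definition separates study drug from a later agent. Under the visible rules, such an event in a placebo subject becomes a placebo IMAE.

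The plan assumes that placebo subjects recur more often, so more of them can enter the overlap period. The placebo IMAE rate would then rise by more than the nivolumab rate, and the apparent excess on nivolumab would fall. Table 6.2.2-1 is titled as supporting warnings and precautions, so a bias towards looking safer deserves attention.

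The efficacy endpoints already deal with the same overlap: SAP 4.1.1 and 4.1.3 truncate DFS and NUTRFS at subsequent anticancer therapy. The visible text gives no reason for treating immune safety differently.

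**Working it through.** The documents state no IMAE rate, so there is no planned figure to reproduce. The arithmetic below only gives the scale.

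**Inputs from the documents** (Protocol 8.1, SAP 5): 350 subjects per arm; control DFS S(t) = 0.32 + 0.68·exp(−0.11t), t in months; nivolumab plateau 47% with a 3-month delay; 43 months of accrual and 17 of follow-up. I read the delay as the control curve up to month 3, then S(t) = 0.47 + (S(3) − 0.47)·exp(−0.11(t − 3)).

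**Check of the model.** With uniform accrual, follow-up at month 60 runs from 17 to 60 months. Averaging 1 − S(t) over that range gives 230.3 placebo and 180.2 nivolumab events, 410.5 in total. The plan states 410, so this reading fits. (Switching the hazard at month 3 instead gives 418.)

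**Subjects with a DFS event by month 12.**
- Placebo: S(12) = 0.32 + 0.68·exp(−1.32) = 0.502; 350 × 0.498 = 174.
- Nivolumab: S(3) = 0.809; S(12) = 0.47 + 0.339·exp(−0.99) = 0.596; 350 × 0.404 = 141 (147 under the hazard switch).
- Ratio of pools: 174/141 = 1.23. Difference: 49.8% − 40.4% = 9.4 points.

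**Assumptions, not in the documents.** A share f = 10-40% of these subjects start a checkpoint inhibitor inside the window, and a proportion r = 5-15% of those have a qualifying IMAE in it. Both are equal across arms.

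| | f·r = 0.10 × 0.05 = 0.005 | f·r = 0.40 × 0.15 = 0.06 |
|---|---|---|
| Added to placebo | 0.25 points (0.9 subjects) | 3.0 points (10.5 subjects) |
| Added to nivolumab | 0.20 points (0.7 subjects) | 2.4 points (8.5 subjects) |
| Shrinkage of risk difference | 0.05 points | 0.57 points |

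The shrinkage is 9.4 × f·r. Widening the assumptions to f = 50% and r = 20% raises the upper end to 9.4 × 0.10 = 0.94 points. The direction reverses only if f·r is more than 1.23 times as high on nivolumab as on placebo.

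**Limits of the pools.** As counts of subjects who stop study drug for a recurrence by month 12 and could start next-line therapy, 174 and 141 are upper bounds. They include deaths. They include intermediate-risk NMIBC, after which Protocol 5.4.1 can allow treatment to continue. They also include subjects who stopped early for another reason and recurred after their 100 days had ended. In the other direction, they leave out recurrences in the 100 days after a completed year. Moving the cut-off to month 12 + 100/30.4375 = 15.3 gives 194 and 155 by the same formulas, and an upper end of (194 − 155)/350 × 0.06 = 0.67 points. The order of magnitude does not change. The sums also assume that no affected subject already has an IMAE in the table.

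**The case against.** **Unseen text.** The SAP table of contents lists 7.6.6 (select AEs) and 7.6.7 (IMAEs), but neither section is in the public text, and text after 7.1.1.1 is blacked out. A truncation rule would most naturally sit there. The general window in SAP 6.1 depends on the analysis, and the all-causality rule for AE tables yields to other specifications. This stands. A reader might infer that the whole plan lacks a cut; the documents support that only for the protocol definition and the visible SAP rules.

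**Other safety tables.** A reader might also take the IMAE table as the trial's main measure of immune toxicity. Protocol 8.4.3 does not name IMAEs. It names AEs, drug-related AEs, SAEs and drug-related SAEs. The visible SAP tables for SAEs, discontinuations, dose modifications and subgroups use the 30-day window, with drug-related versions, and the select-AE onset and resolution analyses use drug-related events. The plan therefore does not rest on one table. These tables do not show, however, how much of an all-causality 100-day IMAE count follows another agent.

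**The 3-point reading.** A reader might take the full 3.0 placebo points as the distortion of the risk difference. That needs both assumptions at their maximum and no such events on nivolumab. Investigators and site staff are blinded, and non-emergency unblinding requests go to the Medical Monitor (Protocol 4.6). The documents describe no route by which next-line immunotherapy would go only to placebo subjects.

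**Conservatism.** Counting all causes for 100 days is a legitimate way to catch late toxicity. Cutting at next-line therapy drops delayed nivolumab events, at a time that depends on recurrence and so on arm. This stands against replacing the definition, but not against a second table.

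**Collection is not analysis.** Protocol 6.2.1 requires nonserious events to be collected "for a minimum of 100 days following the last dose of study treatment". That shows the data will exist; it is not evidence of an analysis error.

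**Conclusion.** The point holds for the protocol definition and the visible SAP rules. As written, they would count immune events from a checkpoint inhibitor started inside the 100-day window under the randomized study drug, placebo included. The likely effect is to understate nivolumab's excess IMAE rate.

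With equal next-line use, the shrinkage is roughly 0.05 to 0.6 percentage points. That rests on the plan's DFS model and on the assumed 10-40% and 5-15%, neither of which the documents supply. Any bias is conditional on such therapy being started and such events occurring.

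Severity is low to moderate. Only the description of safety is affected; alpha, power and DFS are not. This is a cheap improvement.

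**What to change.** First confirm whether SAP 7.6.7 (and 7.6.6 for select AEs) already truncates at subsequent therapy. If it does, a cross-reference from Protocol 6.2.2 is enough.

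If it does not, keep the 100-day all-causality IMAE table and add to the SAP:

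- a supplementary IMAE table by arm, counting only events with onset within 100 days of last dose and before the start of any subsequent anti-PD-1, anti-PD-L1 or anti-CTLA-4 therapy;
- the same table for select AEs wherever the 100-day window is used;
- person-time in the matching exposure-adjusted rates ended on the same date;
- a separate listing, by arm, of events with onset on or after that date.

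The cost is one programmed date comparison and a few outputs. Subsequent therapy is reviewed at both follow-up visits and the survival visits (Protocol Table 5.1-3), and DFS censoring already needs its start date. The downside is that some delayed nivolumab-caused events leave the supplementary table, but they remain in the main table and the listing.
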